#### CONFIDENTIAL

#### 8.1.3.2. Quality of Life Questionnaire for Patients with Aplastic Anemia/PNH

The QLQ-AA/PNH will be completed at Baseline and at the Week 24, 48, 72, and 96 visits. It has 54 items in 12 domains: body image (BI), cognitive functioning (CF), emotional functioning (EF), fatigue (FA), illness intrusiveness (II), fear of progression (PAF), infections (IN), other symptoms (OS), physical functioning (PF), role functioning (RF), social support (SS), and stigmatization (ST). The individual question data from the QLQ-AA/PNH will be listed. Domain scores will not be calculated.

## 8.1.3.3. FACIT-Fatigue Scale

The Functional Assessment of Chronic Illness Therapy (FACIT) Fatigue scale will be administered at Baseline and each clinic visit through Week 96. The FACIT-Fatigue scale has 13 items scored 0-4. A total score will be calculated with range 0 to 52 where 52 indicates complete functionality. See Section 12.4 for the scoring algorithm. The FACIT-Fatigue scale score and change from baseline will be summarized by treatment category and visit. Note that assessments within a transfusion-impacted period will not be summarized but will be presented on the listings.

#### 8.1.4. Other Effectiveness Assessments

#### 8.1.4.1. Clinical Measurements of PNH

Assessment of clinical measurements of PNH are described in Section 10.1.2.

## 8.1.4.2. Subjects with Dose Escalation

The number of subjects who were on each dose level at any time during the study and the total length of time on each dose level will be summarized using descriptive statistics by treatment category. Changes in subject dosing will be listed.

## 8.1.4.3. Discontinuation Due to Lack of Efficacy

Discontinuation due to lack of efficacy was not captured in the eCRF and so cannot be summarized specifically. Captured discontinuation reasons will be summarized on the disposition table.

## 8.1.4.4. Disease Severity

Disease severity will be summarized by treatment category, visit, and by PNH symptom category (fatigue, dyspnea, chest pain/discomfort, difficulty swallowing, abdominal pain, headache, erectile dysfunction, hemoglobinuria, jaundice). The number of subjects with a symptom at each visit will be presented, along with a summary of the number of days with symptoms and the severity.

## 9. SAFETY ANALYSES

Safety endpoints that will be summarized, include the proportion of subjects 1) with TEAEs; 2) who discontinue BCX9930 due to TEAEs; 3) with treatment-emergent serious adverse events (SAEs); 4) with treatment-emergent Grade 3 or 4 AEs; and 5) with treatment-emergent Grade 3 or 4 laboratory abnormalities.

## 9.1. Adverse Events

AEs will be assessed and recorded from the time of signing of the informed consent through the appropriate follow-up period. AEs will be mapped to a MedDRA version 24.0 PT and system organ class (SOC). Relationship to study drug will be assessed as not related, unlikely related, possibly related, probably related, or definitely related. AEs will be graded according to the Division of Microbiology and Infectious Diseases (DMID) Adult Toxicity Table (draft version November 2007, see Protocol Appendix 1). AEs not covered by DMID criteria will be assessed for severity as mild, moderate, severe, or life-threatening, corresponding to toxicity Grades 1 through 4. EOSIs include severe infections that will be identified using the SOC "Infections and infestations" and a reported severity of grade 3 or higher (or missing). In this study the disease related events of BTH and thromboembolic events will be reported as AEs, even if deemed related to the disease under investigation.

If the relationship between the AE or SAE and the study drug is determined to be 'possibly', 'probably', or 'definitely' related, the event will be considered related to the study drug for the purposes of expedited regulatory reporting. Conversely, both events deemed 'unlikely' and those judged 'not related' will be considered not related for regulatory reporting purposes.

TEAEs will be summarized by SOC, PT, and treatment category. TEAEs will also be summarized by SOC, PT, severity, and treatment category. SAEs will be summarized by SOC, PT, and treatment. TEAEs deemed related to study drug, grade 3 and 4 TEAEs, TEAEs leading to treatment interruption or treatment discontinuation, EOSIs, and major adverse vascular events (MAVEs) will be summarized separately by SOC, PT, and treatment category. Summaries will be sorted by descending frequency of SOC and PT. Summaries will be presented chiefly by subject counts, and event counts will also be provided.

AEs, SAEs, MAVEs, and EOSIs will be listed separately by treatment, subject, and start date, showing SOC, PT, and verbatim term.

The duration of AEs in days will be derived and presented in all listings; this value is calculated as (AE stop date/time – AE start date/time). Both start and stop dates must be present to calculate a duration. If an AE start time or end time is missing then include the entire day, but if the AE start date is the treatment start date, then the treatment start time will be used.

Time to first dose reduction either associated with an AE or otherwise, time to discontinuation due to a TEAE, and time to development of drug-related rash will be estimated using the Kaplan-Meier method. Subjects who do not experience a particular event will be censored at the date of the last study visit.

Clinical findings for cutaneous eruptions requiring assessment will be listed.

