14.3.6. Analysis of Clinical Measurements of PNH

Clinical measurements of PNH (eg, LDH, hemoglobin, absolute reticulocyte count, haptoglobin levels, number of blood transfusions, incidence of BTH, incidence of thromboses and major thromboses, AST, total bilirubin, and direct bilirubin) will be summarized by summary statistics, including change from baseline, by treatment group and study visit. Categorical measurements will be summarized with frequencies and percentages by treatment group and study visit.

Breakthrough hemolysis is defined as ≥ 1 new or worsening symptom/sign of intravascular hemolysis (fatigue, hemoglobinuria, abdominal pain, dyspnea, anemia [hemoglobin < 10 g/dL], major adverse vascular event [including thrombosis], dysphagia, or erectile dysfunction) in the presence of lactate dehydrogenase (LDH) ≥ 2 times the upper limit of normal (ULN). Frequency of BTH and time to first BTH will be summarized by treatment group.

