## **3.2.** Study Endpoint(s)

#### **3.2.1. Primary Endpoints**

• Measurement of safety and tolerability by subject incidence of graded TEAEs, laboratory abnormalities, changes to vital signs, ECG results, and physical examination findings.

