## **3.3.** Statistical Hypotheses

This is an open-label Phase 2 study without a control group; therefore, estimation is emphasized above hypothesis testing.

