## 5.4. Data Presentation Conventions

Continuous data will be summarized using the number of subjects with available data, mean, standard deviation (SD), standard error of the mean (SE), median, and minimum and maximum. Categorical data will be summarized using counts and percentages. Percentages are calculated using the total number of subjects per treatment group unless otherwise specified.

Unless otherwise specified, means and medians are formatted to one more decimal place than the measured value, SDs, SEs, confidence interval (CI) limits, and coefficient of variation (CV) to two more decimal places, and minimum and maximum values to the same number of decimal places. For categorical variables, the number and percentage of responses will be presented in the form XX (XX.X%) where the percentage is in the parentheses, except that 100% will be presented to three digits with no decimal. Dates will be formatted DDMMMYYYY and times will be formatted in 24-hour time as HH:MM. Partial dates will be handled as described in Sections 5.7.10 and 5.7.11. P-values and CIs will use a two-sided 0.05 significance level unless otherwise noted; p-values will be presented with three decimal places. Extreme p-values or CIs will be presented as "<0.001" and ">0.999" with the appropriate number of places.

All BCX9930 concentrations will be reported as provided by the concentration vendor.

Wherever possible, data will be decimal aligned.

CONFIDENTIAL

A table of contents at the end of this SAP provides the expected titles and numbers of the tables, listings, and figures of the final report. Changes to titles or numbering in the final report will not necessitate a revision to the SAP, nor will it be considered a deviation from planned analyses. Additional data listings supporting the tables will not be considered a deviation from planned analyses.

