## 7.6. Exposure and Compliance

Subjects will receive kits containing BCX9930 per the schedule of assessments for self-administration at home. The number and percentage of subjects exposed to BCX9930, and the number of days of exposure to BCX9930 in Study 201 and including the parent study will be summarized by treatment category. Individual kit data will be listed by treatment, subject, and date issued.

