#### **10.1.2.** Clinical Measurements of PNH

Continuous clinical measurements of PNH (LDH, hemoglobin, haptoglobin levels, absolute reticulocyte count, AST, total bilirubin, and direct bilirubin) will be summarized by summary statistics including change from baseline and percent change from baseline, by treatment category and study visit. Note that LDH, hemoglobin, haptoglobin, and absolute reticulocyte count that occur within a transfusion-impacted period will not be included in summaries but will be presented in respective listings. Categorical clinical measurements of PNH (number of blood transfusions, incidence of major thromboses) will be summarized with counts and percentages by treatment category (see Section 12.3 for a list of thrombosis events). Incidence of breakthrough hemolysis will be analyzed by the sponsor.

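### The main adverse-event tables and the stand-alone transfusion and major-thrombosis tables are crude counts over follow-up that may end before 144 weeks, with no exposure adjustment and no confidence interval

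*SAP*

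**What the plan says.** - **Primary endpoint (SAP 3.2.1).** "Measurement of safety and tolerability by subject incidence of graded TEAEs, laboratory abnormalities, changes to vital signs, ECG results, and physical examination findings".
- **Adverse-event tables (SAP 9.1).** TEAEs, SAEs, related TEAEs, Grade 3/4 TEAEs, EOSIs and MAVEs are tabulated by system organ class and preferred term. "Summaries will be presented chiefly by subject counts, and event counts will also be provided".
- **Denominator (SAP 5.4).** "Percentages are calculated using the total number of subjects per treatment group unless otherwise specified".
- **Transfusions and thromboses (SAP 10.1.2).** "Categorical clinical measurements of PNH (number of blood transfusions, incidence of major thromboses) will be summarized with counts and percentages by treatment category". Protocol 14.3.6 reads: "Categorical measurements will be summarized with frequencies and percentages by treatment group and study visit".
- **Length of follow-up.** Protocol 7.1 allows up to 144 weeks of treatment, ending sooner if the drug becomes available another way or the sponsor stops development. Protocol 8.3 lets subjects withdraw at any time. SAP 4.1 permits interim analyses as needed for filings and safety updates.
- **Exposure (SAP 7.6).** The plan summarizes "the number of days of exposure to BCX9930 in Study 201 and including the parent study", but no table uses exposure as a denominator.
- **Intervals.** SAP 5.4 sets a two-sided 0.05 convention and SAP 6.2 speaks of tests only if performed. Neither attaches an interval to these summaries, although SAP 3.3 says "estimation is emphasized above hypothesis testing".

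**The concern.** Long-term safety is the primary question. A crude percentage answers how many subjects had the event while they happened to be observed. If observation time varies, that mixes the event rate with time in study. A subject who leaves early without an event counts the same as one who is event-free for 144 weeks.

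The stand-alone transfusion table has the same weakness, because it has no time window at all. SAP 10.1.2 keeps visit for the continuous measures but not for these categorical ones, so it also departs from the protocol.

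Without an interval, a percentage from a small category prints with the same apparent precision as one from a large category.

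**Working it through.** There is no sample-size or precision calculation in the plan to reproduce: about 200 subjects are stated without one (SAP 3.5). Event rates and mean follow-up below are assumptions, because the documents give neither.

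**1. Which summaries are affected.**
- Kaplan-Meier with censoring is planned for dose reduction, discontinuation due to a TEAE and drug-related rash (SAP 9.1), for SARS-CoV-2 infection (SAP 9.1.1), and for potential drug-induced liver injury and serum creatinine above ULN (SAP 12.1, Table 7). Part of SAP 9.1.1 is blanked, so this list may be incomplete.
- Laboratory results, vital signs and ECGs are summarized by time point (SAP 9.2 to 9.4).
- Transfusions enter hematological response at 6-month intervals (SAP 8.1.2).
- What remains is overall and by-term TEAEs, SAEs, Grade 3/4 TEAEs, EOSIs, MAVEs, and the stand-alone transfusion and major-thrombosis summary.

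**2. Crude incidence against follow-up.** With a constant rate λ per year, crude incidence = 1 − exp(−λt), where t = weeks × 7 / 365.25. So 24 weeks is 0.460 years and 144 weeks is 2.760 years.

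| Assumed λ per year | 24 weeks | 144 weeks | Ratio |
|---|---|---|---|
| 0.05 | 2.3% | 12.9% | 5.7 |
| 0.2 | 8.8% | 42.4% | 4.8 |
| 0.5 | 20.5% | 74.8% | 3.6 |

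For example, at λ = 0.2: 1 − exp(−0.2 × 0.460) = 0.088 and 1 − exp(−0.2 × 2.760) = 0.424. The ratios are taken before rounding.

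**3. What a rate would add.** Take 20 events in 20 of 200 subjects. The crude figure is 10% (exact 95% CI 6.2 to 15.0) whatever the follow-up. Per 100 patient-years, with an exact Poisson interval:
- mean observed time 24 weeks: 200 × 0.460 = 92.0 patient-years, giving 100 × 20 / 92.0 = 21.7 (13.3 to 33.6);
- mean observed time 144 weeks: 200 × 2.760 = 552.0 patient-years, giving 100 × 20 / 552.0 = 3.6 (2.2 to 5.6).

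**4. Transfusions.** Six transfusions in 24 weeks are 6 per 24 weeks. Six in 144 weeks are 6 / (144/24) = 1 per 24 weeks. The stand-alone count is 6 either way.

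**5. What an interval would add.** This is about group size, separate from follow-up. With zero events the two-sided exact upper limit is 1 − 0.025^(1/n): 1.8% for n = 200 and 21.8% for n = 15. The 15 is the number who rolled over from Study 101 Part 3 (Protocol 5.4). It is neither a display category nor the planned size.

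**The case against.** The strongest reply is that the SAP does what the protocol asks. Protocol 6.3 defines subject incidence, Protocol 14.3.5 asks for proportions of subjects, and SAP 9 and 9.1 supply them. On that view rates are an addition and correct no error. That stands for the adverse-event tables, and it is why the counts should stay. It does not cover the dropped visit dimension in SAP 10.1.2, which is a plain protocol–SAP difference.

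It is also fair that unequal follow-up is already handled for the events with Kaplan-Meier analyses and, for transfusions, within hematological response. The point excludes those.

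Three stronger readings are tempting, and the documents do not support them:
- **Staggered entry alone makes final follow-up unequal.** Study day counts from each subject's own first on-study dose (SAP 5.7.2), and the final analysis waits for the last subject's final visit (SAP 4.2). Staggered entry matters at an interim cut or a sponsor stop.
- **One C5-inhibitor category is followed for less time and will look safer.** SAP 6.1 assigns subjects from Study 202 and Study 203 to different categories, so entry time and category could be linked. No document says that they are, and no formal comparison between categories is planned.
- **The exposure summary forces a denominator that includes parent-study time.** SAP 7.1 and 7.6 read as giving Study 201 time as well as the longer total, so the right denominator is available. It only has to be named.

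**Conclusion.** The point holds in this bounded form. The named adverse-event tables and the stand-alone transfusion and major-thrombosis summaries have no exposure adjustment and no attached confidence interval, in a study where observation may end well before 144 weeks. SAP 10.1.2 also omits reporting by visit. For the primary endpoint, the gap concerns the TEAE component.

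The 3.6- to 5.7-fold contrast is an illustration. It rests on assumed constant rates of 0.05 to 0.5 per year and an assumed contrast of 24 versus 144 weeks. No minimum or distribution of follow-up is stated. If nearly everyone completes 144 weeks and no interim cut is taken, the distortion is small, but the missing intervals and the missing visit dimension remain. The change should be made because it is cheap and bears on the primary objective.

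**What to change.** **SAP 9.1.** Beside the existing counts, add first-event incidence per 100 patient-years in Study 201, with exact 95% confidence intervals, for TEAEs, SAEs, Grade 3/4 TEAEs, EOSIs and MAVEs. Add exact 95% intervals to the key proportions. Discontinuation due to a TEAE already has a Kaplan-Meier estimate and needs no rate.

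Person-time should run from first on-study dose to first event or to the end of the window in which TEAEs are counted, namely the end-of-study visit, or last contact if earlier. It should not stop at last dose. The TEAE definition in SAP 5.7.8 has no end bound, and adverse events are still reviewed at the visit 3 weeks after last dose (Protocol 11.3.7). Stopping at last dose would count late events with no matching person-time.

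**SAP 10.1.2.** Restore the by-visit summary. State that its denominator is subjects observed in that visit interval, since the default in SAP 5.4 would keep departed subjects in the denominator. Add transfusions and major thromboses per patient-year over Study 201 observed time. If a transfusion-free percentage per 24-week interval is shown, give the number at risk and include subjects who leave mid-interval through a time-to-first-transfusion estimate. Restricting it to completed intervals would drop them.

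**Cost.** SAP wording and some extra table columns. Event, dosing and visit dates are already collected. The drawback is that a rate per patient-year assumes a roughly constant hazard, so the rates supplement the counts and do not replace them.

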14.3.5. Analysis of Safety Variables

Safety endpoints that will be summarized, at a minimum, include the proportion of subjects 1) with TEAEs; 2) who discontinue BCX9930 due to TEAEs; 3) with treatment-emergent SAEs; 4) with treatment-emergent Grade 3 or 4 AEs; and 5) with treatment-emergent Grade 3 or 4 laboratory abnormalities. In addition, the proportion of subjects who received a reduced dose due to tolerability issues at the full dose will be summarized.

Time to dose reduction, time to discontinuation due to a TEAE, and time to development of drug-related rash will be estimated using the Kaplan-Meier method. For those with a drug-related rash, clinical and laboratory findings will be summarized and the proportion of subjects who successfully continued therapy following onset of rash.

AEs will be mapped to a Medical Dictionary for Regulatory Activities (MedDRA) preferred term and system organ class (SOC). The occurrence of TEAEs will be summarized using MedDRA preferred terms, SOCs, and severity. Separate summaries of TEAEs, treatment-emergent SAEs, AEs considered related to study drug, and AEs leading to study drug interruption will be generated. All AEs will be listed for individual subjects showing both verbatim and preferred terms.

Descriptive summaries for vital signs, weight, bedside ECG parameters, and clinical laboratory results will be presented. Laboratory abnormalities will be graded according to the DMID Adult Toxicity Table (Publish Date: Draft, November 2007; Appendix 1).

Any graded abnormality that occurs following the initiation of study drug and represents at least 1-grade increase from the baseline assessment is defined as treatment emergent. The number and percentage of subjects experiencing treatment-emergent graded toxicities will be summarized. Laboratory toxicity shifts from baseline to worst post-baseline assessments will be summarized.

The number and percentage of subjects having elevations in liver enzyme abnormalities (ALT, AST, or bilirubin) in relation to fold above ULN will be summarized according to the Premarketing Clinical Evaluation on Drug-Induced Liver Injury Guidance for Industry.

Clinically significant abnormal morphological ECG findings will be summarized.

The change from baseline in QTcF will be determined by routine ECGs. At each time point ECGs are analyzed, an individual subject's change from baseline will be calculated as:

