#### Study Design:

This is an open-label phase 2 study designed to evaluate the long-term safety of daily oral treatment with BCX9930 in subjects who have participated in a previous BCX9930 trial for PNH and showed a benefit of treatment as determined by the Investigator. The study allows continued access to BCX9930 for enrolled subjects.

Methodology:

Subjects who meet all of the inclusion and none of the exclusion criteria will be enrolled into the study. Study visits will occur at Screening, Baseline/Day 1, Week 4, then every 4 weeks up to Week 96. Once subjects have reached Week 96, subsequent study visits will occur every 8 weeks up to Week 144. Additional visits will be required in the case of rising serum creatinine.

Subjects will receive up to 144 weeks of daily BCX9930.

- For subjects directly rolling over from another BCX9930 study without treatment interruption, no screening visit is required. The final on-study visit assessments in the prior BCX9930 study will serve as the baseline assessments for this study; however, additional relevant baseline assessments for this study may be performed at the final on-treatment visit for the prior study as needed to satisfy enrollment criteria. Enrollment without treatment interruption into the current study will obviate the requirement for a follow-up visit in the previous BCX9930 study.
- Subjects with an interruption of treatment of 1 to 30 days duration will be required to complete a full baseline visit, but no screening visit.
- Subjects with an interruption of treatment of 31 days or greater will be required to complete a full screening visit and then baseline visit.

Prior to Protocol Version 5, the protocol-specified dosing regimen was 500 mg BCX9930 twice daily (BID). Under Protocol Version 5, subjects will receive 400 mg BCX9930 BID.

Safety and tolerability will be evaluated through assessments of TEAEs, laboratory analyses (clinical chemistry, hematology, coagulation and urinalysis), vital signs, ECGs, and physical examination findings. Safety events of special interest, including infections, will be followed.

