#### **Statistical Methods:**

#### Analysis of Safety

Safety endpoints will be summarized and will include the proportion of subjects: with TEAEs; who discontinue due to a TEAE; who receive a reduced dose due to tolerability issues; who experience a treatment-emergent serious adverse event (SAE); who experience a Grade 3 or 4 TEAE; who experience a treatment-emergent, treatment-related adverse event (AE) consistent with a drug rash (eg, rash, maculo-papular exanthem, papular rash); and who experience Grade 3 or 4 laboratory abnormalities.

AEs will be mapped to a Medical Dictionary for Regulatory Activities (MedDRA) preferred term and system organ classification. The occurrence of TEAEs will be summarized using MedDRA preferred terms, system organ classifications, and severity. In addition to severity, AEs and SAEs will also be summarized based on Investigator assessment of relationship to study drug.

Time to dose reduction, time to discontinuation due to a TEAE, and time to development of drug-related rash will be estimated using the Kaplan-Meier method. For those with a drug-related rash, clinical and laboratory findings will be summarized as will the proportion of subjects who successfully continue therapy following onset of rash.

Descriptive statistics for vital signs, weight, and clinical laboratory results will be presented by study visit. Laboratory abnormalities will be graded according to the Division of Microbiology and Infectious Diseases (DMID) Adult Toxicity Table. The number and percentage of subjects experiencing treatment-emergent graded toxicities will be summarized.

Laboratory toxicity shifts from baseline to the worst post-baseline value as well as the last visit will be summarized. The number and percentage of subjects having elevations in ALT, AST, or bilirubin abnormalities in relation to fold above ULN will be summarized according to the United States Food and Drug Administration's Premarketing Clinical Evaluation on Drug-Induced Liver Injury Guidance for Industry.

Clinically significant abnormal ECG findings will be summarized by study visit. Changes from baseline in ECG parameters will also be summarized by study visit. The number and proportion of subjects with clinically important absolute and change-from-baseline thresholds in QTcF will be summarized.

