#### Treatment-emergent increases in

Based on the sponsor's preliminary investigation, reducing the BCX9930 dose to 400 mg BID is anticipated to mitigate the risk of to subjects while maintaining the potential for demonstrating clinical benefit in the PNH patient population.

BCX9930 is expected to provide greater efficacy than the currently available C5 inhibitors by not only preventing intravascular hemolysis, but also by preventing C3 mediated extravascular hemolysis (EVH), thereby reducing symptom burden, reducing hemolysis, including EVH and breakthrough hemolysis (BTH), improving patient function, changing the administration route from intravenous (IV) to oral, and improving health-related quality of life. Study subject selection criteria, dose selection, and study monitoring assessments have been included to optimize benefit and to minimize the risk of toxicities to study participants. Regular monitoring of safety parameters, including AEs, clinical laboratory abnormalities, vital signs measurements, ECGs, and physical examination findings, will ensure that the

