## **3.6.** Treatment

The active ingredient for this study is BCX9930, a small molecule inhibitor of Factor D supplied by BioCryst as 100, 200, and/or 250mg tablets. Earlier versions of this Protocol supplied a white or off-white powder in size 0 hard gelatin capsules. Additional details for the chemical and physical characteristics of BCX9930 may be found in the IB and investigational medical product (IMP) dossier (where applicable).

Subjects on earlier versions of the Protocol started treatment at the same dose level and regimen last administered to that subject in the prior study, and individually escalated their dose level as the physician felt appropriate. As of Protocol version 5, all subjects will receive 400 mg BID, and subjects on lower or higher doses will transition to 400 mg BID for continued participation. Where possible, the BCX9930 doses should be taken at the same times each day as close as possible to 12 hours apart (eg. 8:00 AM and 8:00 PM). If a subject does not take a BCX9930 dose at the scheduled time, the missed dose can be taken up to 6 hours after the scheduled dose time. Subjects will be instructed to bring all drug kits (both unused and used bottles) with them for each study visit.

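### The only dose-reduction curve counts the mandated Version 5 move to 400 mg BID as an event, and the promised tolerability-reduction proportion is missing from the SAP's analysis sections

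*SAP*

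**What the plan says.** **Event.** SAP 9.1 estimates "Time to first dose reduction either associated with an AE or otherwise" by Kaplan-Meier and censors subjects without the event at their last study visit. The SAP does not define dose reduction. The display list (SAP 12.1, Table 7) has one table (14.3.2.10.1) and one figure (14.3.2.10.2) for this analysis, neither split by reason.

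**Mandated change.** The SAP synopsis gives 500 mg BID as the protocol-specified regimen before Version 5. From Version 5, SAP 3.6 says that "all subjects will receive 400 mg BID, and subjects on lower or higher doses will transition to 400 mg BID for continued participation". The SAP Introduction presents this as a programme-level safety measure: "reducing the BCX9930 dose to 400 mg BID is anticipated to mitigate the risk".

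**Promised proportion.** Protocol 14.3.5 says that "the proportion of subjects who received a reduced dose due to tolerability issues at the full dose will be summarized". The SAP synopsis repeats the endpoint, as subjects "who receive a reduced dose due to tolerability issues". SAP section 9 opens its list with "Safety endpoints that will be summarized, include the proportion of subjects 1) with TEAEs" and stops after five items; this one is not among them. SAP 9.1 tabulates "TEAEs leading to treatment interruption or treatment discontinuation" but has no matching summary for reduction.

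**The concern.** A time-to-dose-reduction curve in a safety section will be read as a measure of tolerability. As defined, it also registers the date on which an amendment reached each subject above 400 mg BID. If many subjects were switched, the curve mainly shows the timing of the amendment.

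Two further losses follow. A switched subject has used up the first reduction, so a later one made for an adverse event cannot appear on the curve. The summary that would have shown tolerability reductions by themselves has also dropped out of the analysis sections. Safety and tolerability are the primary endpoint of this study, yet neither the SAP body nor its display list names an output showing how often subjects were reduced for tolerability.

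**Working it through.** The plan states no figure to reproduce. The check has a textual part and an illustration of size.

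**Does the switch meet the event definition?**
- SAP 9.1 takes in reductions that are not linked to an adverse event.
- SAP 3.6 moves subjects on higher doses down, and the Introduction itself describes the change as reducing the dose.
- No text excludes the switch or censors at it.
- Only subjects above 400 mg BID are affected. Those on lower doses move up, and later entrants start at 400 mg BID.

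A programmer who follows the stated rule would therefore count each downward switch.

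**Is the proportion anywhere else?** SAP 8.1.4.2 summarises the number of subjects and the time on each dose level, and lists dose changes. Neither summary is by reason. No Table 7 title covers the proportion.

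**Inputs for size.** Protocol 5.4 reports 15 subjects entering from Study 101 Part 3, and SAP 3.5 plans about 200. The number above 400 mg BID at Version 5 is not given. Assume that all 15 were, that all switched by Week 96, and that switching is independent of tolerability. The share switched, p, is then 15/200 = 7.5%, 15/50 = 30%, 15/30 = 50%, or 100% if no one else enrolled.

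**Formula.** With tolerability-reduction rate r per person-year, the true Week 96 risk is 1 − exp(−r × 96/52.18). The all-cause estimate is 1 − (1 − p) × exp(−r × 96/52.18).

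Example, r = 0.05: exp(−0.0920) = 0.912, so the true risk is 8.8%. With p = 0.075, 1 − 0.925 × 0.912 = 15.6%.

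| Assumed r per 100 person-years | True risk | p = 7.5% | p = 30% | p = 50% | p = 100% |
|---|---|---|---|---|---|
| 2 | 3.6% | 10.8% | 32.5% | 51.8% | 100% |
| 5 | 8.8% | 15.6% | 36.2% | 54.4% | 100% |
| 10 | 16.8% | 23.0% | 41.8% | 58.4% | 100% |

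With no tolerability reductions at all, the formula gives p itself.

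**Simulation of the remedy.** Settings: 2,000 replicates, r = 5 per 100 person-years, switch uniform over Weeks 12 to 96, 15% dropout per year, follow-up to Week 144. The reason-specific curve ignores the switch and follows subjects through it.

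| Switched | All-cause, Week 96 | Reason-specific, Week 96 | Mean tolerability reductions missed by the all-cause curve |
|---|---|---|---|
| 15 of 200 | 15.7% | 8.8% | 0.86 of 20.9 (4%) |
| 15 of 50 | 36.2% | 8.9% | 0.91 of 5.25 (17%) |
| 15 of 30 | 54.5% | 8.9% | 0.91 of 3.15 (29%) |
| 15 of 15 | 99.7% | 8.7% | 0.86 of 1.56 (56%) |
| 50 of 100 | 54.3% | 8.8% | 2.93 of 10.4 (28%) |

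The reason-specific curve recovers the true 8.8%. If the rate halves after the switch, it reads 8.7%, 8.4%, 7.9%, 6.9% and 7.9% in the same order, an average over two dose periods. The all-cause figures then move by no more than 0.2 points.

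**The case against.** The best counter-argument is that counting the switch is an inference. SAP 3.6 calls it a transition, and protocol 10.5.1 discusses dose reduction in the setting of investigators managing adverse events. A programmer could leave the switch out. That is possible, but the SAP 9.1 definition reaches beyond adverse events and contains no exclusion, so inclusion is the more natural reading.

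An all-cause curve is also what the protocol planned. That stands, and is why the curve should stay. But protocol 14.3.5 pairs it with the tolerability proportion, and the SAP kept only the curve.

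The gap might be filled elsewhere. Display specifications are in a separate document (SAP 12.2), Table 14.3.1 could carry the proportion, SAP 12.1 lets displays be split without a revision, and SAP 5.2 requires notes defining derived variables. None of this commits anyone to a split or to the proportion. A note can tell readers that the curve is all-cause but does not separate the events.

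The size is illustrative. SAP 3.6 says earlier subjects began at their prior-study dose and escalated individually, so some of the 15 may have been at or below 400 mg BID. Conversely, subjects rolling over from other studies before Version 5 could add to the number switched. The 100% case needs no further enrolment.

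Two more points stand. No decision rule rests on this curve in a descriptive, uncontrolled study. And the protocol's proportion refers to a full dose, whose meaning changed with Version 5, so restoring it without a definition would leave it unclear.

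**Conclusion.** The concern holds and should be fixed before the final analysis. Under the SAP as written, the single dose-reduction curve combines mandated switches with tolerability reductions, and the promised tolerability proportion has no stated place in the analysis sections or display list.

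The direction is clear: the curve overstates tolerability reductions whenever anyone was switched down. The amount depends on the share switched, which the documents do not give. With 7.5% to 50% switched and 2 to 10 tolerability reductions per 100 person-years, the Week 96 overstatement runs from about 6 percentage points (23.0% against 16.8%) to about 48 (51.8% against 3.6%). The loss of later reductions is smaller in absolute terms: on average about 0.9 with 15 switched and 2.9 with 50 of 100 switched, over 144 weeks. Share switched, rates, dropout, switch timing and independence are all assumptions.

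**What to change.** 1. Add a Kaplan-Meier analysis of time to first reduction with a recorded adverse-event or tolerability reason. State that the Version 5 switch is not an event and that follow-up continues through it. A change on the switch date counts only if an adverse event has dose reduction as its recorded action. Report event counts and person-time before and after the switch.
2. Keep the all-cause curve as supplementary, with Version 5 switches counted on their own row.
3. Put the tolerability-reduction proportion into SAP section 9 and Table 7. Define its denominator, and what full dose means for the analysis before and after Version 5.

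The cost is SAP wording, one extra table and one extra figure for the new curve, and a display entry for the proportion. No new data should be needed: the protocol calls for the reason for each reduction (10.5.1) and the action taken for each adverse event (13.9.2), and SAP 7.6 refers to dose escalation and reduction records. SAP 8.1.4.3 shows that another planned reason was not captured in the eCRF, so the reason field should be checked. If it does not separate amendment switches, dosing dates and action taken can identify them.

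The drawback is that following subjects through the switch averages over dose levels; the before-and-after counts make that visible.
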